 **The primary objective:**

Recession depth which will be measured before the surgical procedure, then after 3 and 6 months.

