#### **14 - Sample size**

The aim of this study is to evaluate the use of coronally advanced flap and subepithelial connective tissue graft with or without platelet rich fibrin regarding Recession depth. In a previous study by **Keceli et al., 2015** the expected difference in Recession depth decrease from baseline between 2 groups is  $0.45\pm0.38$ mm. Using power 80% and 5% significance level we will need to study 12 in each group to be able to reject the null hypothesis that the population means of the experimental and control groups are equal. This number is to be increased to 14 in each group to correct for non-parametric usage and increased again to 17 to compensate for possible losses during follow up. Sample size calculation was achieved using PS: Power and Sample Size Calculation software Version 3.1.2 (Vanderbilt University, Nashville, Tennessee, USA ).

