**18-Data collection methods****18a-Data collection method:**

The phone numbers and address of the patient included in the study will be recorded from them or extracted from the patient's file which will be available at [name] office , the one responsible for filing system in the Oral Medicine and Periodontology department. The data will be collected by dr [name], whether personal or numerical. They will be stored on excel sheets as an electronic copy and printed hardcopy sheets. The outcome data will be collected at 0, 3 and 6 months. Numerical data will be presented as mean and standard deviation

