## **20- Statistical method:**

Data management and statistical analysis will be performed using Statistical Package for Social Sciences (SPSS) vs. 21. Numerical data will be summarized using means and standard deviations or medians and ranges. Data will be explored for normality using Kolmogrov-Smirnov test and Shapiro-Wilk test. Categorical data will be summarized as percentages. Comparisons between two groups and over time will be done by 2 way analysis of variance for repeated measures. If the time factor is not considerable, comparisons between the two groups for normally distributed numeric variables will be done using the Student's t-test while for non-normally distributed numeric variables will be done by Mann-Whitney test. A p-value less than or equal to 0.05 will be considered statistically significant. All tests will be two tailed.

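### As usually run, the planned repeated-measures ANOVA drops any patient missing one of the 0-, 3- and 6-month readings, and the plan does not say how incomplete records are handled

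*Combined protocol and SAP*

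**What the plan says.** The primary objective is "Recession depth which will be measured before the surgical procedure, then after 3 and 6 months", and section 18a confirms the schedule: "The outcome data will be collected at 0, 3 and 6 months". Section 20 names the software as "Statistical Package for Social Sciences (SPSS) vs. 21" and the method as follows: "Comparisons between two groups and over time will be done by 2 way analysis of variance for repeated measures". It does not name the SPSS procedure or say which contrast is primary.

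Section 20 also has a fallback: "If the time factor is not considerable, comparisons between the two groups for normally distributed numeric variables" are to use Student's t-test, with the Mann-Whitney test for non-normal variables.

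Losses are expected. Section 14 raises 12 per group to 14 for possible non-parametric testing, and that figure is "increased again to 17 to compensate for possible losses during follow up". Sections 11-c and 18b try to prevent losses with reminder calls, a possible home visit and possible transport fees. No section defines an analysis set, an intention-to-treat rule, or a method for missing readings.

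**The concern.** Classical repeated-measures ANOVA (in SPSS, GLM Repeated Measures) takes one row per patient with one column per visit, and removes any row with an empty cell. With three visits, two kinds of patient leave the analysis although useful data exist for them:

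- a patient who withdraws after month 3, whose 3-month reading has already been taken;
- a patient who misses only month 3, whose 6-month reading is at the trial's stated horizon.

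Two things are at stake. The first is waste: the analysis uses fewer patients than have a 6-month value. The second matters more. If loss is related to the early result and differs between arms, the patients with complete records are no longer the randomised groups, and the estimated difference can move in either direction. Enlarging the sample protects power but does nothing against selective loss.

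**Working it through.** **Inputs from the plan (section 14).** Difference in recession depth decrease 0.45 mm; SD 0.38 mm, read here as the common SD; 80% power; 5% level, two-sided (section 20); 12, then 14, then 17 per group.

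**The plan's own figures reproduce.** n = 2 × (1.96 + 0.84)² × 0.38² / 0.45² = 11.2, so 12. Then 12 / 0.864 = 13.9, so 14. An allowance of 15% gives 14 / 0.85 = 16.5, so 17. The allowance amounts to 3 of 17 (17.6%).

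**Who is kept: an assumed example.** Per arm, 3 of 17 withdraw after month 3 and 2 miss only month 3. Complete records: 17 − 3 − 2 = 12. Patients with a 6-month value: 17 − 3 = 14. Patients with some post-operative value: 17. Of 34 × 3 = 102 scheduled readings, 2 × (3 + 2) = 10 are missing, so 92 exist. The complete-record analysis uses 24 × 3 = 72.

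**Power by complete records per arm** (two-sample t, noncentral): 17 gives 91.7%, 14 gives 85.4%, 13 gives 82.5%, 12 gives 79.2%, 11 gives 75.2%. The allowance alone leaves 14. If a further share m misses only month 3, the expected number is 17 × (1 − 0.176) × (1 − m). For m = 5%, 10% and 15% this is 13.3, 12.6 and 11.9, so power is about 82%, 79% and 75% (rounding down), although 14 per arm still have a 6-month value. The documents give no value for m.

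**Precision and bias.** Assumed: 17 per arm, 3 lost per arm after month 3, and a correlation ρ of 0.6 to 0.9 between 3- and 6-month results. The documents give neither the loss pattern nor ρ.

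*Random loss.* There is no bias. The complete-record SE is 0.38 × √(2/14) = 0.144 (about 0.143 in simulation). With all 3-month readings used, SE = 0.38 × √(2 × [ρ²/17 + (1 − ρ²)/14]) = 0.139, 0.135 and 0.133 at ρ = 0.6, 0.8 and 0.9. Simulation gives 0.140 to 0.132. The gain is about 3% to 7%.

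*Selective loss in controls only, random in the PRF arm.* The three lowest of 17 standard-normal values sum to −4.14 on average, so removing them raises the mean of the other 14 by 4.14 / 14 = 0.296 SD. If selection is on the 3-month result, the 6-month control mean rises by ρ × 0.38 × 0.296 = 0.067, 0.090 and 0.101 mm. If selection is on the 6-month result itself, it rises by 0.38 × 0.296 = 0.112 mm.

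| Loss pattern | Complete records (mm) | All readings used (mm) |
|---|---|---|
| Random in both arms | 0.45 | 0.45 |
| Worst three at month 3 in both arms | 0.45 | 0.45 |
| Worst three controls at month 3 only | 0.38, 0.36, 0.35 | 0.45 |
| Worst three controls at month 6 only (unseen) | about 0.34 | about 0.37, 0.41, 0.43 |

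Where three values are shown they are for ρ = 0.6, 0.8 and 0.9. Simulation agrees with the formulas, and the last column is from simulation. By symmetry, if only the PRF arm lost its worst three at month 3, the complete-record difference would be too large: 0.45 + 0.067 = 0.52 to 0.45 + 0.101 = 0.55 mm.

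**The case against.** A reader might infer that every incomplete patient is certain to be excluded from the primary comparison. The documents do not go that far. The SPSS procedure is not named, and SPSS MIXED would keep incomplete patients. The primary contrast is not defined. The t-test/Mann-Whitney branch would keep a 6-month value when only month 3 is missed. These points stand, and they make the claim conditional. They do not remove it: section 20 names an analysis of variance, not a mixed model, and the fallback applies only when time has no considerable effect. That is unlikely for recession depth before and after root-coverage surgery. The fallback at 6 months would also still discard the 3-month value of a patient lost later.

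A reader might also infer that the trial's estimate will be 15% to 22% too small (0.067 / 0.45 to 0.101 / 0.45). That is an assumed extreme, with exactly the three worst controls leaving and PRF losses random. No section supports that pattern. Patients are unblinded (section 17), but they can see their own recession whichever arm they are in, so differential attendance is conjecture. A milder pattern, with three controls drawn at random from the worse half at month 3, gives about 0.41 to 0.39 mm. Even the worst-case shift of 0.10 mm is smaller than the SE of about 0.14 mm.

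The planned increase to 17 covers its own allowance (85.4% power at 14 per arm), and the retention measures make an isolated missed visit less likely. Both are fair. Neither says what happens to an incomplete record.

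Finally, the full recovery of 0.45 mm follows from making loss depend only on an observed value. When loss depends on the unseen 6-month result, a mixed model corrects only partly.

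**Conclusion.** The concern holds in conditional form. In its usual form the stated method discards patients with one missing reading, the plan expects losses, and nothing in it handles incomplete records.

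The certain cost is small: an SE about 3% to 7% larger than it need be under random loss. Power falls below 80% only if month-3-only misses, at rates the documents do not give, are added to the full allowance. The possible bias is zero if loss is random or equally selective in both arms, and about 0.07 to 0.10 mm in the assumed one-arm worst case on 3-month results. These sizes rest on SD 0.38 mm, a difference of 0.45 mm, 3 of 17 lost per arm and a correlation of 0.6 to 0.9. The plan should be changed because a better method is available at almost no cost, not because bias has been shown.

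**What to change.** In section 20, replace the repeated-measures ANOVA for recession depth with a linear mixed model (SPSS MIXED):

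- **Data:** the 3- and 6-month readings of all randomised patients with at least one post-operative reading, analysed as randomised.
- **Terms:** arm, visit, arm-by-visit, and baseline recession depth as a covariate, with unstructured covariance. Adjusting for baseline keeps the analysis in line with section 14, which is sized on the decrease from baseline.
- **Reported result:** the 6-month arm contrast.
- **Rules to state:** a missed 3-month visit does not remove the 6-month reading, and the model assumes data are missing at random given the readings observed.
- **Reporting:** losses by arm and time, including patients lost before month 3, who contribute no post-operative reading to the model.
- **Sensitivity:** one simple analysis in which loss is related to outcome.

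The software, visits and data stay the same. The cost is a few sentences in section 20 and slightly more analysis work.

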## **21-Data monitoring**

-No formal data monitoring committee will be needed since it is a study with known minimal risks.

## **22-Harms**

Any temporary or permanent adverse effect will be recorded and documented.

No Harms are expected.

## **23-Auditing**

No auditing is to be done since no harms are expected.

## **24-Research ethics approval**

-This protocol and the template informed consent form will be reviewed by the Ethics Committee of Scientific Research -Faculty of Oral and Dental Medicine- Cairo University

## **25-Protocol amendments**

Any modifications to the protocol which may have an impact on the conduct of the study, potential benefit of the patient or may affect patient safety, including changes of study objectives, study design, sample sizes, study procedures, or significant administrative aspects will require a formal amendment to the protocol. Such amendment will be agreed upon by the Council of Periodontology Department.

## **26-Consent:**

Researcher will introduce the trial to patients and provide full explanation of its aim and benefits in plain language. Patients will then be able to have an informed discussion with the researcher. Researcher will obtain written consent from patients willing to participate in the trial. All consent forms will be translated into Arabic.

## **27-Confidentiality**

All study-related information will be stored securely. All participant information will be stored in locked file cabinets in areas with limited access. All reports, data collection, process, and administrative forms will be identified by a coded ID [identification] number only to maintain participant confidentiality. All records that contain names or other personal identifiers will be stored separately from study records identified by code number. All local databases will be secured with password-protected access systems.

## **28- Declaration of interests**

If there will be any conflict of interest it will be declared.

## **29-Access to data**

The principal investigator and the supervisors will be given access to the data sets. All data sets will be password protected. To ensure confidentiality, data dispersed to project team members will be blinded of any identifying participant information.

### **30-Ancillary and Post Trial Care**

All patients will be followed up for one year after the clinical trial is over.

### **31-Dissemination policy**

[figure not shown]
- Study results will be published as partial fulfillment of the requirements for Doctorate degree in Periodontology.
- Topics suggested for presentation or publication will be circulated to the authors.

### **(Keceli *et al.*, 2015)Appendix:**

#### **1. Pain Scale**

Filled in by the patient after being given instructions about charting by the dental operator.

### مقياس الألم

اليوم	التاريخ
اليوم (0) يوم العملية	
اليوم (1)	
اليوم (2)	
اليوم (3)	
اليوم (4)	
اليوم (5)	
اليوم (6)	
اليوم (7)	
اليوم (8)	
اليوم (9)	
اليوم (10)	
اليوم (11)	
اليوم (12)	
اليوم (13)	
اليوم (14)	

Filled in by the patient

مقياس رضا المريض بعد اجراء العملية

(1-7)

الاسم:

هل تود ان تجرى لك العملية مرة اخرى ؟

هل تناصح بها للاخرين ؟

الى اى مدى انت راض عن النتائج ؟

### 3. Root coverage esthetic score

The RES system evaluates five variables 6 months following surgery: gingival margin (GM), marginal tissue contour (MTC), soft tissue texture (STT), mucogingival junction (MGJ) alignment, and gingival color (GC). The clinical esthetic evaluation is performed without magnification. Zero, 3, or 6 points are used for the evaluation of the position of the gingival margin, whereas a score of 0 or 1 point is used for each of the other variables

- GM: -Zero points = failure of root coverage (gingival margin apical or equal to the baseline recession)
  - 3 points = partial root coverage;
  - 6 points = CRC.
- MTC: -Zero points = irregular gingival margin (does not follow the CEJ).
  - 1 point = proper marginal contour/ scalloped gingival margin (follows the CEJ).
- STT: - Zero points = scar formation and/or keloidlike appearance .
  - 1 point = absence of scar or keloid formation.
- MGJ: - Zero points = MGJ not aligned with the MGJ of adjacent teeth.
  - 1 point = MGJ aligned with the MGJ of adjacent teeth.
- GC: -Zero points = color of tissue varies from gingival color at adjacent teeth.
  - 1 point = normal color and integration with the adjacent soft tissues.

Thus, the ideal esthetic score is 10.

Zero points are assigned if the final position of the gingival margin is equal or apical to the previous recession depth (failure of root coverage procedure), irrespective of color, the presence of a scar, MTC, or MGJ. Zero points are also assigned when a partial or total loss of interproximal papilla (black triangle) occurred following the treatment.

